8.3 Handling of Missing and Incomplete Data

8.3.1 Patterns of Missing Data

Subjects may be missing specific data points for various reasons. In general, data may be missing due to a subject's early withdrawal from study, a missed visit, or non-evaluability of a data point or an endpoint at a particular point in time. In the Data Issue Identification and Resolution (DIIR) process, queries will be made to the sites to distinguish true missing values from other unknown values (eg, due to measurement processing error). All attempts will be made to capture missing or partial data for this trial prior to the data cutoff date.

The frequency and pattern of missing data for efficacy endpoints will be assessed through descriptive summaries of the measurements over time.

There will be no imputation for missing data except the incomplete date imputation for AE and concomitant medication.

8.3.2 Handling of Incomplete Dates

Adverse event and concomitant medication (eg, lipid regulatory medication) with completely or partially missing start dates will be queried. After the issue is queried, if the date is still incomplete with year only or year and month only, the start date will be imputed as described in table below.

Imputation Rules for Incomplete Dates

	Missing	Imputation	Exception
Start date (AE and concomitant medication)	Day	1	Default to Study Day 1 if an event starts the same year and month as Study Day 1
	Day/Month	1-Jan	Default to Study Day 1 if an event started the same year as Day 1

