4.1 Inclusion and Exclusion Criteria

4.1.1 Inclusion Criteria

All Subjects:

101 Subject has provided written informed consent or subject assent prior to initiation of any study-specific activities/procedures.

and/or

102 Subject's legally acceptable representative has provided informed consent when the subject is legally too young to provide informed consent and the subject has provided written subject assent based on local regulations and/or guidelines prior to any study-specific activities/procedures being initiated.

Subjects with HeFH:

103 Completed Study 20120123 while still on assigned investigational product and did not experience a treatment-related serious adverse event.

Subjects with HoFH:

104 Male or female, ≥ 10 to ≤ 17 years of age at time of enrollment (includes the year after the subject completes the 17th year after birth but not the day of completing the 18th year after birth).

105 Diagnosis of HoFH by genetic confirmation or a clinical diagnosis based on a history of an untreated LDL cholesterol concentration > 500 mg/dL (13 mmol/L) together with either xanthoma before 10 years of age or evidence of heterozygous familial hypercholesterolemia in both parents.

106 Subject must be on a low-fat diet and receiving background lipid-lowering therapy (such as statins, cholesterol absorption inhibitors, bile acid sequestrants, nicotinic acid, or combinations thereof).

107 Lipid-lowering therapy, including statin dose, must be unchanged for ≥ 4 weeks prior to LDL-C screening; fibrates must be stable for at least 6 weeks prior to screening.

108 Fasting LDL-C at screening ≥ 130 mg/dL (3.4 mmol/L) as determined by central laboratory.

109 Fasting triglycerides ≤ 400 mg/dL (4.5 mmol/L) by central laboratory at screening.

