5.1 Study Timepoints

Enrollment Date

The enrollment date is defined as the date collected on the Subject Enrollment eCRF.

Study Day 1

For each subject, Study Day 1 is defined as the first day of investigational product administration. If a subject never received IP, then Study Day 1 is defined as the date of enrollment.

Study Day

For each subject, and for a given date of interest, study day is defined as the number of days since Study Day 1:

Study day = (date of interest – Study Day 1 date) + 1.

If the date of interest is prior to the Study Day 1:

Study day = (date of interest – Study Day 1 date), so that the day prior to Study Day 1 is study day -1.

First Dose Date of Investigational Product

For each subject, the First Dose Date of Investigational Product is defined as the first administration date of the IP as recorded on the IP administration eCRF.

Last Dose Date of Investigational Product

For each subject, the Last Dose Date of Investigational Product is defined as the date of the last administration of the IP:

If the last dose was administered in-clinic, then the Last IP Dose Date is the last start date captured on the IP Administration (In-Clinic) eCRF page.

If the last dose was administered at a non-investigator site location, then the Last IP Dose Date is defined as the final dose date reported by the subject on the Non-Clinic Final Investigational Product Dose Date eCRF page.

End of Study (EOS) Date for Each Subject

End of study for each subject is defined as the last day on which the enrolled subject in this study completes the end-of-study visit (week 80) or terminates the study early. The date will be recorded on the End of Study eCRF page.

Study End Date for the Overall Study

The study end date is defined as the date when the last enrolled subject has completed the end-of-study visit (week 80) (ie, last subject last visit).

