9.6.12 Exposure to Other Protocol-required Therapy

The number and proportion of subjects receiving selected lipid regulating medications captured on the Lipid Regulating Concomitant Medications eCRF will be summarized for baseline use and post-baseline use. The subject incidence of changes in lipid regulating medications during the treatment period will also be provided ([Appendix C](#)).

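### SAP 8.3.2 sets a year-only medication start in the Day 1 year to first dose, whatever the stop date or documented prior use

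*SAP*

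**What the plan says.** SAP 8.3.2 gives its scope as follows: "Adverse event and concomitant medication (eg, lipid regulatory medication) with completely or partially missing start dates will be queried". Imputation comes after the query, and only "if the date is still incomplete with year only or year and month only". One table then serves adverse events and medication alike:

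- Day missing: the 1st of the month, except "Default to Study Day 1 if an event starts the same year and month as Study Day 1".
- Day and month missing: 1 January, except "Default to Study Day 1 if an event started the same year as Day 1".

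SAP 5.1 fixes the anchor: "Study Day 1 is defined as the first day of investigational product administration". SAP 8.3.1 says that incomplete dates are the only thing imputed in this study, so no later rule corrects the result.

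SAP 9.6.12 draws on a dedicated eCRF page for lipid-regulating medication. It summarises baseline and post-baseline use, and adds: "The subject incidence of changes in lipid regulating medications during the treatment period will also be provided". It gives no rule for deciding which records are baseline and which are post-baseline.

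For HoFH subjects, Protocol 4.1.1 (criterion 107) says: "Lipid-lowering therapy, including statin dose, must be unchanged for ≥ 4 weeks prior to LDL-C screening". Protocol 6.3 expects background therapy to stay the same through screening and the study unless a change is clinically necessary.

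**The concern.** The Day 1 default suits adverse events. An event of uncertain date is pushed into the treatment-emergent period, which agrees with SAP 5.3, where any event that cannot be clearly classified counts as treatment-emergent. A later date is not automatically the cautious choice for a medication. There the same default can produce a date that other data on the same subject contradict: a recorded stop before Day 1, or a record at screening or in the parent study showing that the drug was already in use.

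The output at stake is SAP 9.6.12, the only section that plans a summary of changes in lipid drugs. The study has no control arm, so a reader will use that summary to judge whether the week 80 LDL-C change reflects evolocumab added to stable therapy. With about 10 HoFH subjects, one false change would move that cohort's incidence by about 1/10, or 10 percentage points.

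**Working it through.** **1. The rule as written.** Let D be Study Day 1 and S the imputed start.

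- Year Y only: S = D if Y is the year of D; otherwise S = 1 January of Y.
- Year Y and month M only: S = D if both match D; otherwise S = the 1st of M.

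The stop date, ongoing status and earlier use do not enter.

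**2. Applied to constructed records.** D = 17 Sep 2018 is assumed for illustration.

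| True dates | Reported start | Imputed start | Effect |
|---|---|---|---|
| From 3 May 2014 | 2014 | 1 Jan 2014 | Stays before Day 1 |
| From 20 Dec 2017 | 2017 | 1 Jan 2017 | Stays before Day 1 |
| From 5 Jan 2018 | 2018 | 17 Sep 2018 | Moved 255 days later, to Day 1 |
| 20 Feb to 1 Mar 2018 | 2018 | 17 Sep 2018 | Start is 200 days after the stop |
| Stopped 10 Sep 2018 | Sep 2018 | 17 Sep 2018 | Start is 7 days after the stop |
| 20 Nov to 1 Dec 2018 | 2018 | 17 Sep 2018 | Stays on study, 64 days early |

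The fourth and fifth rows are impossible dates, whatever table is later built on them. In the third row, if the drug is an HoFH subject's qualifying background therapy, a Day 1 start also conflicts with criterion 107.

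**3. Reach.** Only starts in the calendar year of D are moved, so the shift is at most 364 days (1 January to 31 December, non-leap year).

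- HeFH: a drug begun before the 24-week parent study started at least 168 days before D. It can share D's calendar year only if D is on or after 18 June, which is 197/365 = 54% of calendar days.
- HoFH: a drug begun at least 28 days before D can share its year only if D is on or after 29 January, which is 337/365 = 92% of calendar days.

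**4. Illustrative size.** The documents give neither a rate of partial dates nor a history of drug starts, so everything in this step is assumed. Take D uniform over the year and the drug started a uniform time between g and H years before D. For H of at least 1, the chance that the start falls in D's calendar year is

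P = (1 − g)² / [2(H − g)].

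- HoFH, g = 28/365 = 0.0767: (0.9233)² = 0.8525. For H = 2, P = 0.8525/3.8466 = 0.222. For H = 8, P = 0.8525/15.8466 = 0.054.
- HeFH, g = 196/365 = 0.5370 (24 weeks plus an assumed 4): (0.4630)² = 0.2144. For H = 2, P = 0.2144/2.926 = 0.073. For H = 8, P = 0.2144/14.926 = 0.014.

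Suppose 10% to 30% of those starts remain year-only after query, and each subject has one background drug.

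- HoFH: 0.054 × 0.10 = 0.5% up to 0.222 × 0.30 = 6.7%. Times 10 subjects, that is about 0.05 to 0.7 records.
- HeFH: 0.014 × 0.10 = 0.14% up to 0.073 × 0.30 = 2.2%. Times 111 subjects, that is about 0.2 to 2.4 records.

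This counts continuing background drugs only. It does not estimate how many stopped drugs would get a start after their stop.

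**The case against.** A reader might infer that long-standing background statins become on-study starts and that their users would appear under Appendix C as taking no statin at baseline. The documents do not support either inference.

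- A year-only start in any earlier calendar year goes to 1 January of that year and stays pre-study. Only drugs begun in the Day 1 year are moved.
- Where SAP 5.2 ties baseline to first dose, it turns on when a value was collected, not on a drug's start date. Appendix C likewise refers to statin use at baseline. Concomitant therapy is recorded at HoFH screening (Protocol Table 2), and criterion 106 requires background therapy by then. A statin on that record was documented before first dose, whatever start is later imputed.
- SAP 9.6.12 gives no date cut, so a CRF flag could decide baseline use. A false treatment-period change is possible but not shown.

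The other side can also say that dates are queried first, that all analyses are descriptive, and that no LDL-C change is computed from a medication start date. All of that stands and keeps the point small.

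A further objection concerns the remedy. Dropping the Day 1 default for all medication would date a drug truly added later in the Day 1 year to 1 January and hide a genuine on-study addition. That also stands, so the default should be restricted rather than removed. None of these arguments removes the start-after-stop dates, which follow from the table alone.

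**Conclusion.** The rule has a small but definite defect. For a medication start that is still partial after query and falls in the Day 1 year (or the Day 1 month, if only the day is missing), it ignores information that can contradict the imputed date. A drug stopped before Day 1 then gets a start after its stop; this rests on no assumption. A background lipid drug begun earlier in the Day 1 year can be dated to first dose.

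Whether that second effect reaches a reported table depends on SAP 9.6.12 being programmed from start dates, which the SAP leaves open. The number of records is likely small: on the assumptions shown, under one background record for HoFH and at most two or three for HeFH. The documents give no count. No lipid or adverse event result is shown to change. This is a low-severity point, worth correcting because the remedy is nearly free.

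**What to change.** Split the table in SAP 8.3.2 by record type.

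- **Adverse events:** keep the Study Day 1 default.
- **Concomitant and lipid-regulating medication:** use the Study Day 1 default only when the stop date is on or after Day 1 (or the drug is ongoing) and the drug was not recorded as in use before first IP in screening or parent-study records. Otherwise impute the 1st of the month, or 1 January.
- **All medication:** never impute a start later than the recorded stop date.

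On the constructed records, and taking the 5 January drug as recorded at screening, its start becomes 1 January 2018. The drug stopped on 1 March also gets 1 January, and the one stopped on 10 September gets 1 September, each before its stop. The November addition, with no earlier record of use, stays at Day 1, so genuine on-study additions are still counted.

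The cost is a few lines of SAP text and a small programming change, including a look-up of screening and parent-study medication records.

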8.4 Detection of Bias

This study has been designed to minimize potential bias. For subjects rolling over from study 20120123, central laboratory results of the lipid panel, as well as ApoA1, ApoB, Lp(a), and PCSK9 will be blinded until the subject has reached week 12 in Study 20120124. For these subjects, vitamins A, D, E and K will also be blinded until the study 20120123 database is locked. In addition, investigators and staff involved with this trial and all medical staff involved in the subject's medical care should refrain from obtaining lipid panels until week 12 in Study 20120124 and, if a lipid panel is drawn, all reasonable

steps must be undertaken to avoid informing the subject and study personnel of the results.

Factors that may bias the results of the study include:

- Major protocol deviations likely to impact the analysis and interpretation of the efficacy endpoints

Important protocol deviations likely to impact the analysis and interpretation of the safety and efficacy endpoints will be tabulated in the Clinical Study Report (CSR).

8.5 Outliers

Various methods, including univariate summaries, histograms, scatter plots, box plots, and line graphs, may be used to identify outliers in key safety and efficacy variables. Extreme data points will be identified during the blinded review of the data prior to database lock. Such data points will be reviewed with clinical data management to ensure accuracy. The **interim analysis and** primary analyses may include outliers in the data. Sensitivity analyses may be undertaken if extreme outliers for a variable are observed.

8.6 Distributional Characteristics

Statistical analyses in this study are descriptive in nature. No statistical inference is planned. No distributional characteristics will be assessed in this study.

8.7 Validation of Statistical Analyses

Programs will be developed and maintained and output will be verified in accordance with current risk-based quality control procedures.

Tables, figures, and listings will be produced with validated standard macro programs where standard macros can produce the specified outputs.

The production environment for statistical analyses consists of Amgen-supported versions of statistical analysis software; for example, the SAS System version 9.4 or later.

9. Statistical Methods of Analysis

9.1 General Considerations

The interim analysis will be conducted when all the enrolled subjects in the study have opportunity to experience 28 weeks of investigation product exposure or have early terminated from the study. At that time, the database related to the interim analyses of the study (on or before the data cutoff date) will be cleaned,

processed and a snapshot will be taken. All analyses for the interim analyses will be based on the interim data on or before the data cutoff date. The scope of the interim analyses includes all endpoints specified in the protocol amendment 4 dated 14 May 2020.

To evaluate the safety, tolerability and effect of 80 weeks of SC evolocumab when added to standard of care in pediatric subjects 10 to 17 years of age with HeFH or HoFH, the primary analysis will be conducted when all the enrolled subjects in the study have either completed all the scheduled visits up to and including week 80 or have early terminated from the study. At that time, the database will be cleaned, processed and locked. All endpoints will be analyzed based on this snapshot.

All analyses **for both the interim and primary analyses** will be descriptive. Missing data will not be imputed for safety endpoints. Statistical analyses in this open label study are descriptive in nature. No statistical inference or missing value imputation is planned. **Unless specified otherwise, the FAS will be the default analysis set in this study and data will be summarized by cohort (HeFH and HoFH) as well as by the randomized treatment group of the parent study for HeFH cohort (as defined in [section 5.3](#)). Due to the open-label study design, all analyses for both interim and primary analyses will also be summarized by cohort for the overall subjects.**

Subject disposition, demographics and baseline characteristics will be summarized.

Summary statistics for continuous variables will include the number of subjects, mean, median, standard deviation or standard error, first quartile (Q1), third quartile (Q3), minimum, and maximum. For categorical variables, the frequency and percentage will be given.

Unless specified otherwise, the FAS will be the default analysis set in this study and subjects will be summarized by 3-level groups defined in [section 5.3](#).

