7. STUDY PROCEDURES

7.1 Schedule of Assessments

Approved

Table 2. Schedule of Assessments

Study Day / Week / Other Timepoint ^a	Screening		D1/Parent Study EOS	W4 ^c (±3d)	W12 (±7d)	W24 (±7d)	W36 (±7d)	W48 (±7d)	W60 (±7d)	W72 (±7d)	W80 (EOS) (±7d)
	HoFH	HeFH ^b									
General Procedures											
Informed parental/guardian consent/permission and subject consent/assent – HoFH subjects	X										
Informed parental/guardian consent/permission and subject consent/assent – HeFH subjects		X	X								
Enrollment			X ^d								
Medical history	X										
Vital Signs (sitting BP, HR)	X	X	X	X	X	X		X			X
Review for AEs/SAEs/ADEs	X ^e	X ^e	X	X	X	X	X	X	X	X	X
Concomitant therapy	X	X	X	X	X	X	X	X	X	X	X
Dietary instruction	X	X	X		X	X	X	X	X	X	
Physical exam (including neurologic examination)	X										X
Height, weight, cIMT, Tanner staging			X ^f			X		X			X
Neurocognitive assessment (Cogstate battery)	X		X ^g			X		X ^g			X
12 lead ECG			X								X
Central Laboratory^h											
Fasting lipids ^h	X	X ⁱ	X		X			X			X
ApoA1, ApoB100, Lp(a) ^h			X		X						X
PK (evolocumab), PCSK9			X		X						X
Chemistry, including fasting glucose ^h	X	X			X			X			X
Hematology	X	X						X			X
Estradiol (females) / testosterone (males)		X ⁱ	X								X
HbA1c, FSH, LH, ACTH, DHEA-S, cortisol, hsCRP, fasting vitamins A/D/E/K ^l		X ⁱ	X								X
CK	X	X ⁱ	X		X			X			X
Biomarkers (blood) ^k			X								X
Anti-evolocumab antibodies			X								X
HCV testing ^l	X										
HCV viral load ^l			X					X			X
Serum pregnancy ^m	X	X									X
Urine pregnancy ^m			X ^{n, o}	X	X	X	X	X	X	X	
Urinalysis, urine microalbumin, urine creatinine, urine albumin/creatinine ratio			X								X

Footnotes displayed on the next page of the Table

Approved

Table 2. Schedule of Assessments

Study Day / Week / Other Timepoint ^a	Screening		D1/Parent Study EOS	W4 ^c (±3d)	W12 (±7d)	W24 (±7d)	W36 (±7d)	W48 (±7d)	W60 (±7d)	W72 (±7d)	W80 (EOS) (±7d)
	HoFH	HeFH ^b									
Investigational Product											
Screening placebo AI/Pen (HoFH subjects only)	X										
IP administration on-site / instruction as needed			X	X	X	X	X	X	X	X	
AI/Pen or AMD dispensation ^p			X ^q	X	X	X	X	X	X	X	
AI/Pen or AMD reconciliation					X	X	X	X	X	X	X

Page 2 of 2

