7.2 Interim Analysis and Early Stopping Guidelines

The interim analysis will be conducted when all the enrolled subjects in the study have opportunity to experience 28 weeks of investigation product exposure or have early terminated from the study. At that time, the database related to the interim analyses of the study will be cleaned, processed and a snapshot will be taken. Unless specified otherwise, the FAS will be the default analysis set in this

study. Similar to the primary analysis, the interim data will be summarized by cohort (HeFH and HoFH). Statistical analysis in this interim analysis is descriptive in nature for all safety and efficacy endpoints if applicable. No statistical hypotheses testing or missing value imputation is planned. There is no study stopping rule for either futility or efficacy and the current design or execution of the study will continue without any changes regardless of the result of the interim analysis.

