9.5.2 Analyses of Secondary Efficacy Endpoint(s)

Descriptive statistics of percent change from baseline will be provided for the following efficacy parameters at week 80

- LDL-C
- Non-HDL-C
- ApoB
- Total cholesterol/HDL-C ratio
- ApoB/ApoA1 ratio

In addition, the descriptive statistics in change from baseline will be provided for LDL-C at week 80.

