Appendix A. Analytical Study Week Assignments

Selected endpoints will be summarized by scheduled study visits in descriptive analyses. Since the actual visits may not exactly coincide with their scheduled visit day, the actual visit day is mapped to the study visit generally by non-overlapping consecutive intervals covering the entire time continuum, with scheduled visit time being the center of each interval. The mapping intervals for all distinct schedules are summarized in the following tables.

Tests / Analytical Visit Window	Week 4	Week 12	Week 24	Week 36	Week 48	Week 60	Week 72	Week 80
Target day	29	85	169	253	337	421	505	561
Vital Signs (sitting BP, HR)	(1, 56]	(56, 126]	(126, 252]		(252, 448]			(448, EOS]
Physical exam (including neurologic examination)								(1, EOS]
Height, weight, cIMT ^a , Tanner staging			(1, 252]		(252, 448]			(448, EOS]
Neurocognitive assessment (Cogstate battery) - HoFH			(1, 252]		(252, 448]			(448, EOS]
Neurocognitive assessment (Cogstate battery) - HeFH			(1, 364]					(364, EOS]
12 lead ECG								(1, EOS]
Lipids		(1, 210]			(210, 448]			(448, EOS]
ApoA1, ApoB100, Lp(a)		(1, 322]						(322, EOS]
PK (evolocumab), PCSK9		(1, 322]						(322, EOS]
Chemistry, including glucose		(1, 210]			(210, 448]			(448, EOS]
Hematology					(1, 448]			(448, EOS]
Estradiol (females) / testosterone (males)								(1, EOS]
HbA1c, FSH, LH, ACTH, DHEA-S, cortisol, hsCRP, vitamins A/D/E/K								(1, EOS]
CK		(1, 210]			(210, 448]			(448, EOS]
Biomarkers (blood)								(1, EOS]
Anti-evolocumab antibodies								(1, EOS]
HCV viral load					(1, 448]			(448, EOS]
Urinalysis, urine microalbumin, urine creatinine, urine albumin/creatinine ratio								(1, EOS]

^a cIMT assessments conducted up to and including study day 28 are considered baseline values.

Handling multiple records assigned to an analytical study week:

If there is more than one record in a study week interval, the analytical record for that specific study week will be defined as the record closest to the scheduled visit day of that specific study week ($7 \times \text{study week} + 1$). If two records are equidistant from the scheduled day, then the earlier record will be chosen. If there are multiple records on the same day, the last record will be used.

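### Interim week-80 summaries of hormones, hsCRP, ECG and neurologic examination over-represent subjects who withdrew, because ongoing subjects cannot yet contribute

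*SAP*

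**What the plan says.** - **Trigger.** SAP 7.2 and 9.1 and protocol 10.3.2 place the interim when all enrolled subjects "have opportunity to experience 28 weeks of investigation product exposure" or have terminated early.
- **Scope.** SAP 9.1: "The scope of the interim analyses includes all endpoints specified in the protocol amendment 4 dated 14 May 2020". SAP 7.2 is softer: "Statistical analysis in this interim analysis is descriptive in nature for all safety and efficacy endpoints if applicable". Neither section lists the visits to be reported.
- **Endpoints.** SAP 9.5.2: "Descriptive statistics of percent change from baseline will be provided for the following efficacy parameters at week 80". Hormone and cIMT changes and enzyme abnormalities are also week-80 endpoints (SAP 9.6.3).
- **Schedule.** Protocol Table 2 places lipids, CK and chemistry (with AST and ALT) at weeks 12, 48 and 80 after Day 1, and ApoB at weeks 12 and 80. Hormones, hsCRP and ECG are taken on Day 1 and then only at week 80. The neurologic examination is at screening and end of study.
- **Withdrawal.** Protocol 7.2.2 asks for the week-80 procedures at the time of withdrawal, if possible.
- **Mapping.** In SAP Appendix A the row "HbA1c, FSH, LH, ACTH, DHEA-S, cortisol, hsCRP, vitamins A/D/E/K" has one window, (1, EOS], assigned to week 80. The estradiol/testosterone, ECG and physical/neurologic examination rows have the same window. Lipids and CK enter week 80 only after day 448, and ApoB only after day 322.
- **Missing data.** Missing values are not imputed (SAP 9.1).

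**The concern.** For the parameters with a single (1, EOS] window, a subject can have a week-80 value at the interim in two ways: by reaching week 80 before the cutoff, or by withdrawing at any time and having the closing procedures done. A subject who is still on study and short of week 80 has no scheduled value. A withdrawal in the first months is thus labelled week 80, while subjects who stayed on treatment for the same time are absent. The resulting column is selected by enrolment date and by withdrawal.

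SAP 5.3 adapts the adverse-event and exposure definitions to the data cutoff, but nothing equivalent is done for visit-based endpoints. Nor is there a rule on whether percentages, such as abnormal neurologic findings, are taken over the full analysis set or over subjects assessed. With the full set as denominator, subjects who have had no post-Day-1 examination would count as having no finding. At stake is how the interim results for these pediatric safety measures are read.

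**Working it through.** **1. Calendar.** Appendix A sets the target day at 7 × week + 1. For weeks 4, 12, 24, 36, 48, 60, 72 and 80 this gives 29, 85, 169, 253, 337, 421, 505 and 561, which matches all eight stated days. Week 28 is 7 × 28 + 1 = day 197.

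**2. Visits guaranteed by day 197.** Count a visit if its target day plus the 7-day visit window is no later than day 197. Week 24 qualifies (169 + 7 = 176). The week-36 window opens only at 253 − 7 = day 246.

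| Parameter | Scheduled after Day 1 | Guaranteed at interim |
|---|---|---|
| Lipids, CK, AST/ALT | 12, 48, 80 | 12 |
| ApoB | 12, 80 | 12 |
| Height, weight, Tanner, cIMT | 24, 48, 80 | 24 |
| Cogstate | 24, 80 (HoFH also 48) | 24 |
| Hormones, hsCRP, ECG, neurologic examination | 80 | none |

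**3. Who can have reached a later visit.** Week 80 is 561 − 197 = 364 days (52 weeks) after the trigger day, and week 48 is 337 − 197 = 140 days (20 weeks) after it. The documents give no accrual period, so assume uniform accrual over E weeks, a cutoff 28 weeks after the last enrolment, and no dropout. The share with time to reach week w is (E + 28 − w)/E, bounded by 0 and 1.

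| E (weeks) | Week 80: (E − 52)/E | Of 124 | Week 48: (E − 20)/E |
|---|---|---|---|
| 52 | 0% | 0 | 62% |
| 78 | 33% | 41 | 74% |
| 104 | 50% | 62 | 81% |
| 156 | 67% | 83 | 87% |
| 208 | 75% | 93 | 90% |

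**4. Over-representation in the (1, EOS] parameters.** Call the week-80 share s. A leaver whose withdrawal procedures are done contributes with probability 1, and a subject who stays contributes with probability s. The ratio is 1/s: 1/0.33 = 3 at 78 weeks, 1/0.50 = 2 at 104 weeks and 1/0.75 = 1.3 at 208 weeks. At 52 weeks or less, s = 0 and only leavers contribute. The number of leavers is not given, so their share of the column cannot be computed.

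**5. Lipids, CK and ApoB.** A leaver's lipid or CK record up to day 448 goes to week 12 or week 48. The first day that counts as week 80 is 449 = 7 × 64 + 1, so anyone in that window needs E + 28 ≥ 64, that is E ≥ 36 weeks. For ApoB the first day is 323 = 7 × 46 + 1, so E ≥ 46 − 28 = 18 weeks. Only late leavers can join those who reached week 80.

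**The case against.** The strongest reply is that most of what the interim can usefully show is already planned. SAP 9.5.3 summarises lipids at each protocol-specified visit, which delivers week 12. SAP 9.6.3 reports growth and Tanner staging at week 24, and SAP 9.6.10 reports Cogstate at each administration. SAP 7.2 carries an if-applicable qualifier, continuous summaries show the number of subjects, and SAP 9.2 reports ongoing subjects, the cutoff date and discontinuations by reason. The interim is descriptive, has no stopping rule and does not alter conduct. All of this stands, and it keeps the point small. It does not answer the mapping: an n beside a week-80 mean does not tell the reader how many values were taken at withdrawal.

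A second reply is that the (1, EOS] window applies equally at the primary analysis. That is true, but by then every subject who stayed has had the chance to reach week 80. The imbalance between leavers and stayers is specific to the interim.

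Stronger readings that a reader might infer are not supported:

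- *That the interim has no on-study hormone or ECG data.* Both are taken on Day 1. What is missing is a scheduled value between Day 1 and week 80.
- *That with accrual of a year or less every interim week-80 value comes from a leaver.* For lipids and CK, leavers up to day 448 are mapped elsewhere, and with accrual under 36 weeks the cell is empty.
- *That the subset must be small.* With long accrual it could be most of the sample. The original protocol is dated May 2015 and the amendment adding the interim May 2020. These dates do not fix the accrual period, but they give no reason to favour the shortest case.

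**Conclusion.** The point holds, at minor severity. At the interim, the week-80 summaries of hormones, hsCRP, ECG and neurologic examination combine early enrollers who reached week 80 with leavers from any time. Leavers are over-represented because ongoing subjects cannot contribute. For lipids and CK this is confined to records after day 448, and for ApoB to records after day 322, so those week-80 values come mainly from early enrollers.

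The schedule and mapping facts rest on the documents alone. The size does not: the range of 0% to 75% able to reach week 80 assumes uniform accrual over 52 to 208 weeks without dropout, and no dropout figure is available. The primary endpoint, week-12 lipids by visit, and week-24 growth, Tanner and Cogstate results are not affected. The consequence is a risk of misreading some interim tables, not a risk to trial conduct or to the primary analysis.

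**What to change.** In SAP 9.1 and Appendix A, state for the interim that:

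- week-48 and week-80 values are summarised only in subjects whose Day 1 makes that visit due by the data cutoff;
- percentages use subjects assessed as the denominator;
- each such table gives the numbers due, observed and early-terminated;
- withdrawal values taken before the week-80 visit window (before day 561 − 7 = 554) appear in a separate early-termination row and are not labelled week 80.

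The separate row keeps the safety observations from subjects who stopped, so nothing is discarded. The cost is SAP wording, a smaller n in the interim week-80 columns and one extra row. The interim would also depart from the Appendix A mapping used at the primary analysis, so the SAP should state that difference. No added assessments and no change of cutoff are needed.
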